What is the effect of Berberine on the gene expression of IL-1 β , TNF- α and NLRP3, in peripheral blood cells in individuals with exogenous obesity?

9. Objectives

General objective:

To determine the effects of Berberine on gene expression of cytokines IL-1 β , TNF- α and NLRP3 in individuals with exogenous obesity.

Specific Objectives:

1. To form groups diagnosed with exogenous obesity.
2. To evaluate anthropometric parameters
3. To evaluate biochemical parameters
4. To quantify the expression (mRNA) of NLRP3, IL-1 β and TNF- α
5. To establish the differences in gene expression between individuals with exogenous obesity and control subjects.

10. Hypothesis

Berberine inhibits gene expression of NLRP3, IL-1 β and TNF- α in individuals with exogenous obesity.

11. Material and methods

Type of study:

An experimental, analytical, longitudinal, prospective study of comparative groups was carried out.

Study subjects

Ninety patients with type I and II obesity will be selected, as well as 30 control subjects (healthy adults), who agreed to be donors of a peripheral blood sample, 2 tubes (1: biochemistry, 2: gene expression) channeled to the Obesity Program unit (Comprehensive Medical Service, ESM, IPN), with the following selection criteria.

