12.1. Selection criteria

Inclusion

Human peripheral blood obtained from adult donors with the following characteristics:

- Patients with $\text{BMI} \geq 30\text{kg/m}^2$
- With risk factors for type 2 diabetes (history of diabetic parents or siblings, sedentary habits)
- Fasting blood glucose $\leq 126 \text{ mg/dL}$ or glycosylated hemoglobin $< 6.5\%$
- Controlled arterial hypertension
- >18 years of age
- Accept and sign the informed consent

No inclusion

- Hypersensitivity to the components of the formula
- History of hypoglycemic episodes
- History of obesity of endogenous origin
- History of serious psychological, psychiatric, eating or neurological disorders

- History of hyperthyroidism, heart disease, diabetes, liver or kidney failure, glaucoma, epilepsy
- Pregnancy or lactation

Exclusion criteria

- Pregnancy
- Diabetics
- Presenting any serious adverse effect
- Patients who decide to withdraw from the protocol

Elimination

- Samples contaminated during processing
- Lysed blood samples
- Coagulated blood simple.

Variable Description

Independent Variable

Berberine

Category: quantitative.

Measurement scale: ratio.

Measurement unit: 500 mg with excipient q.s.

Operational definition: the tested dose of Berberine was 500 mg, given to patients for 3 months.

Dependent

Gene expression of IL-1 β , TNF- α and NLRP3.

Category: quantitative.

Measurement scale: discrete, continuous.

Measurement unit: arbitrary units.

Operational definition: Cytokines were determined with commercial qPCR equipment/reagents, and their arbitrary units/relative expression were determined by a specific standard curve for each one.

Observation method: open.

Sampling method: non-probabilistic sampling of consecutive comparative groups that met the selection criteria, until reaching the sample size that constituted the study groups (patients with exogenous obesity).

Operational description of the study: Berberine has been provided by the Medix laboratory, in 500 mg capsules, to treat patients for 3 months.

Study groups

The individuals will be distributed into four groups:

- Group 1. Individuals with exogenous obesity: nutritional plan intervention for lifestyle change.
- Group 2. Individuals with exogenous obesity: nutritional plan intervention, moderate controlled aerobic exercise for lifestyle change.

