- Group 3. Individuals with exogenous obesity: nutritional plan intervention, moderate aerobic exercise and Berberine phytopharmaceutical. With biweekly sessions for 3 months.
- Group 4. Normal-weight individuals without intervention.

Blood samples were taken after informed consent from the participants, they were informed of the intervention and the group to which they belonged, they were also taken at the end of the study.

Procedure

In the selection, obtaining information, anthropometry and blood biochemistry, the subjects of the study will be asked for authorization and their participation will be requested after a detailed explanation of the risks and benefits of the protocol, obtaining signed informed consent.

Obtaining the samples

The universe of the study will be individuals from 19 to 55 years of age with exogenous obesity; they will be recruited in the Obesity Projects area of the Postgraduate Studies and Research section of the Higher School of Medicine of the National Polytechnic Institute, referred by the Comprehensive Medical Service.

Each participant will be asked in writing to enter the study, each one was identified, and a clinical history was prepared with anthropometric measurements: weight, percentage of body fat, percentage of visceral fat, height, BMI. Peripheral blood will also be taken for blood biochemistry and messenger RNA extraction and qPCR tests to determine gene expression of NLRP3, IL-1 β and TNF- α .

Biochemical tests.

Peripheral blood samples will be evaluated by an external laboratory.

Blood samples will be collected at the beginning and three months after treatment. Participants were called at 7 am, after fasting for at least 8 hours, and the sample was collected in Vacutainer tubes (BD, USA), added with ethylenediaminetetraacetic acid (EDTA) to prevent coagulation. 4 mL of blood was taken from everyone; from there, 1 mL of Trizol (Sigma-Aldrich, USA) was added to 2 2 mL tubes with 100 μ L per tube. The blood was vortexed for 30 s and stored at -70 °C until processing. The rest of the blood was stored at -20 °C.

Anthropometric evaluation

The somatometry of each participant will be determined by wearing light clothing and without shoes: weight, height, % body fat, % visceral fat.

Height

It will be defined as the distance between the vertex and the support plane.

- Instrument: Stadiometer (Seca mod. 208).
- The measurement will be expressed in cm with a precision of 1 mm.

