“Low-calorie” Mediterranean diet: This is the model supported by SEEDO because it represents this balanced and healthy approach, with a low intake of saturated and trans fatty acids and added sugars, and a high consumption of vegetable fiber and monounsaturated fatty acids. Its health benefits, including mortality, are clearly established in the literature.

High-protein diet: Based on the satiating effect and less loss of lean mass. The intake is increased to >1.2 g/kg/day, with a minimum intake of 90 g daily.

Nutritional Management

The nutritional management plan in this project will be aimed at improving the lifestyle and quality of life of patients, as well as reducing their body weight. This intervention will be done according to the nutritional management for obesity developed by nutritionists from INCMNSZ.

The goals of the nutritional plan were to establish healthy eating habits with a 10-15% reduction in body weight during treatment.

Nutritional Consultations

The consultations will be biweekly to evaluate body weight, anthropometry and adherence to the nutritional regimen, in addition to monitoring the modification of eating habits.

Clinical-nutritional history

In this clinical history, the lifestyle of the patients will be evaluated, the activities from the time they will wake up until bedtime will be questioned, their physical activities, allergies or intolerances, eating habits such as: meal times, tastes, preferences, quantities, type of food preparation, economic amount allocated, places of food, if they ate with electronic distractions, among others, to know the needs of each participant and adequately prescribe the food plan.

Food frequency

A food frequency survey from ENSANUT 2012 will be applied to learn about eating habits and determine the consumption of energy, important macro and micronutrients. The same survey analyzes and reports the results when capturing the data. With the evaluation of the diet and the anthropometric, biochemical, clinical, dietary and economic indicators, a nutritional diagnosis and the degree of obesity of each patient were established.

Energy expenditure

After the diagnosis, the prescription of the individualized food plan was prepared. The basal energy expenditure (BEE) was calculated with the Harris Benedict formula, and the current body weight.

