While the total energy expenditure (TEE) was estimated from the physical activity of everyone by multiplying the BEE by the physical activity factor, according to the category of each one.

Energy prescription

A negative balance was induced to decrease 1kg of body weight per week, reducing from 500 to 1,000 Kcal per day. The caloric deficit was determined from the TEE for their current weight, the daily energy intake of the participants where the number of calories was calculated having the total energy expenditure minus 20% to obtain homogeneity in all participants.

Dietary distribution and composition.

The nutritional distribution with 50% carbohydrates was recommended, 10% simple carbohydrates, from fruit consumption, while the distribution with 30% fats was recommended, 10% saturated fats, and finally the distribution with 20% protein was half of animal origin and half of vegetable origin. The meal plans were adapted according to the requirements of each participant.

Each meal plan contained sample menus and an additional food exchange brochure, which contained the food groups and their equivalents, depending on whether the participants' weight decreased or the number of portions of each food group was maintained, as well as the calories of each nutritional plan.

The number of mealtimes was distributed in 5: 3 main meals (breakfast, lunch and dinner) and two additional snacks (morning and afternoon).

The lists of the Mexican System of Equivalents and the Institutional Program for the Prevention and Control of Diabetes Mellitus, IMSS, were used to prepare a list of portions

of the most consumed/common foods that were organized into food groups. The objective was to facilitate the participants' practice of new eating habits.

Anthropometric Evaluation

It allowed us to identify alterations in the nutritional status of each participant, as well as the associated risks; the anthropometric variables that were evaluated at the beginning of the program, every 15 days and at the end allowed us to assess the changes in the participants beyond weight loss, granting nutritional plans according to the specific needs for their anthropometric, biochemical, clinical, dietary, economic assessment and according to their family history.

Phytopharmaceutical

Therapeutic indications

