The thermocycler was programmed with the following scheme: preincubation for one cycle of 10 minutes at 95°C; the reaction for 45 consecutive cycles (denaturation at 95°C for 10 seconds, annealing at 60°C for 30 seconds and extension at 72°C for 1 second) and the final incubation at 40°C for 30 seconds.

Table 5. Oligonucleotide sequences used to determine gene expression.

Gen	Proteins	Sequences	Concentration
NLRP3	Proteína 3 que contiene dominios NACHT, LRR y PY	F: 5' GCA AGA CTT TGA CAA CAT GC3' R: 3'CAC CTG TTG TGC AAT CTG AAG5'	10nM
TNF- α	Factor de necrosis tumoral alfa	F: 5' CAGCCTCTCTCCCTTGAT3' R: 3'GCCAGAGGGCTGATTAGAGA5'	10nM
IL-1 β	Interleucina 1 beta	F: 5' TTG GGT AAT TTT TGG GAT CTT AC3' R: 3'CTG TCC TGC GTG TTG AAA GA5'	10nM
B-actina	Gen constitutivo	F: 5' AGC CAC ATC GCT CAG ACA C3' R: 3'GCC CAA TAC GAC CAA ATC C5'	10nM

Statistical analysis

The values of each determination are expressed as the mean \pm SE. The differences between the groups were calculated with ANOVA. Differences between the groups will be determined by using Student's T test. In all tests, a value less than or equal to 0.05 was considered significant.

Ethical aspects

The study will be of lower than minimum risk, since no blood was obtained from the participants in quantities greater than the limit established by the Regulations for Research on Human Beings of the General Health Law. The project was evaluated,

approved and accepted by the Research and Ethics Committee of the Higher School of Medicine of the National Polytechnic Institute.

The study was carried out in accordance with the ethical principles:

- Declaration of Helsinki of the WMA - Ethical principles for medical research involving human beings¹²⁶.
- Written and signed informed consent as stipulated in article 21 of the General Health Regulations on Health Research¹²⁷.
- As stipulated in article 17 of the General Health Regulations on Health Research, this project is classified as minimal risk¹²⁷.
- The protocol was carried out in compliance with the recommendations established in NOM-087-ECOL-SSA1-2002, which addresses matters related to Environmental Protection and Environmental Health; Biological-infectious Hazardous Waste¹²⁸.

Material Resources

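### Weight and body composition are measured about seven times per patient, but the analysis names no time point, baseline adjustment or within-patient correlation

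*Combined protocol and SAP*

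**What the plan says.** Evaluating anthropometric parameters is specific objective 2. Anthropometric Evaluation describes "the anthropometric variables that were evaluated at the beginning of the program, every 15 days and at the end" and says that these values served to assess change in the participants as well as to tailor the nutritional plans. Nutritional Consultations agrees: "The consultations will be biweekly to evaluate body weight, anthropometry and adherence to the nutritional regimen". The variables listed are "weight, height, % body fat, % visceral fat", with BMI derived from weight and height. The intervention lasts three months.

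The Statistical analysis section has four elements:
- a summary as mean ± SE;
- "The differences between the groups were calculated with ANOVA";
- a second sentence beginning "Differences between the groups will be determined by using", which names Student's t test;
- the threshold "a value less than or equal to 0.05 was considered significant".

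It does not mention a time factor, a repeated-measures or paired form, change scores, a baseline covariate, the visit at which groups are compared, or missing visits. The exclusion criteria under Selection criteria include patients who decide to withdraw. The plan does not say whether their recorded weights stay in the analysis.

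**The concern.** Seven correlated values per patient can be analysed in several ways that all comply with the text: one chosen visit, the last visit in completers, change from baseline, each visit separately, or all visits together. These differ in precision, in who is included and, for the last, in validity. A reader of the results could not tell which was used. This matters in practice because the Abstract already reports significant anthropometric results with berberine.

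Two consequences need sizing. The first is what is lost or distorted when only the final visit is compared. The second is what would happen to the type I error if every visit were entered as a separate, independent value.

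**Working it through.** The plan gives no power calculation, SD, expected weight loss or dropout rate, so it has no figure of its own to reproduce.

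**Inputs.** From the documents: measurement every 15 days over about 90 days; threshold 0.05; "Ninety patients with type I and II obesity will be selected, as well as 30 control subjects". Assumed: 90/3 = 30 per obese group (the split is not stated), a two-sided test, and a within-patient correlation ρ of 0.5-0.95.

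**Number of occasions.** 90/15 + 1 = 7. Fourteen-day steps over 84 days give 84/14 + 1 = 7. A separate end visit at day 91 or 92 would make 8.

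**If all visits were pooled as independent.** The design effect is D = 1 + (m − 1)ρ with m = 7, the SE is understated by a factor √D, and the true type I error is 2[1 − Φ(1.96/√D)]. The simulated columns use 4,000 runs with 30 per group and equal correlation between visits.

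| ρ | D | √D | t test, formula | t test, simulated | three-group ANOVA, simulated |
|---|---|---|---|---|---|
| 0.5 | 4.0 | 2.0 | 0.33 | 0.33 | 0.48 |
| 0.7 | 5.2 | 2.3 | 0.39 | 0.40 | 0.57 |
| 0.8 | 5.8 | 2.4 | 0.42 | 0.43 | 0.61 |
| 0.9 | 6.4 | 2.5 | 0.44 | 0.45 | 0.64 |
| 0.95 | 6.7 | 2.6 | 0.45 | 0.44 | 0.65 |

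Pooling the six changes from baseline as independent gives about 0.30 across this range.

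**If one value per patient is used.** The type I error stays at 0.05 and the cost is precision. Set the variance of an unadjusted end value to 1. Then:
- change from baseline has variance 2(1 − ρ);
- the baseline-adjusted end value has 1 − ρ²;
- the baseline-adjusted mean of six later visits has (1 + 5ρ)/6 − ρ².

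| ρ | change | adjusted end value | adjusted mean of six |
|---|---|---|---|
| 0.5 | 1.00 | 0.75 | 0.33 |
| 0.8 | 0.40 | 0.36 | 0.19 |
| 0.95 | 0.10 | 0.098 | 0.056 |

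The last column answers the three-month question only if the effect is constant over time. For the three-month contrast, most of the gain over an unadjusted end value comes from the baseline. The interim visits add mainly through patients who lack the final one.

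**If patients without a final visit are dropped.** The simulation assumed 30 per arm, mean loss 5 kg, true extra loss 2.0 kg, slope SD 3.5 kg, residual SD 1 kg and dropout driven by the latest observed loss, with 300 replicates per scenario. A second simulation used the same inputs with differently tuned dropout.

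| Dropout in the two arms | completers, kg | repeated-measures model, kg |
|---|---|---|
| 28% v 18% | 1.7 | 2.05 |
| 20% v 14% | 1.9 | 2.0 |
| 26% v 21% (second) | 1.80 | 1.99 |
| 17% v 12% (second) | 1.88 | 2.00 |
| 23% v 19%, weaker dependence (second) | 1.95 | 1.99 |

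The completer estimate has an SE of about 1.05 kg, so the Monte Carlo error of each mean is about 1.05/√300 = 0.06 kg. A shortfall of 0.3 kg is clear of that, 0.1 kg barely so, and 0.05 kg not.

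**The case against.** A reader might infer that the plan treats all visits as independent and that its tests therefore run at a 42-45% type I error. The documents do not support this. No sentence says that visits are pooled. The wording about every determination belongs to the descriptive mean ± SE sentence, and the two test sentences speak only of differences between groups. ANOVA or a t test on end values, changes or slopes would be valid, and unqualified ANOVA could even mean a repeated-measures form, though nothing in the text says so.

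A reader might also infer that the berberine difference in weight is biased. That needs dropout to depend on weight response, for which the documents give no evidence. In the simulated scenarios the bias is at most about 0.3 of an SE and shrinks the difference, so it would not manufacture a benefit. Those scenarios also favour the mixed model, which is unbiased by construction when dropout depends on observed loss. They do not test withdrawal for serious adverse effects, which the exclusion criteria also list.

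The interim visits have a care purpose too, in adherence monitoring and diet adjustment, so leaving them out of a model is not an error in itself.

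All of this stands, and it narrows the point. It does not supply the missing specification: the plan still fixes no time point, baseline adjustment or treatment of repeated and missing values for an outcome it measures about seven times.

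**Conclusion.** The point holds as a gap in specification with a better method available, not as a demonstrated error. A last-visit comparison is sound for type I error as far as the repeated visits are concerned. It costs precision, omits patients without a final visit, and can be biased by about 0.1-0.3 kg towards the null if dropout follows weight response. That range rests on the assumed effect, SDs and dropout above. The 33-45% type I error for a t test is conditional on pooling, which the plan does not state, and on ρ of 0.5-0.95.

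The reach is limited to specific objective 2 in Groups 1-3. Group 4 receives no intervention and may have no 15-day visits. Gene expression, the subject of the general objective and hypothesis, is sampled only at the start and at three months. The change should be made, but the main outcome does not depend on it.

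**What to change.** For weight, BMI, % body fat and % visceral fat in Groups 1-3, replace the stated tests with a linear mixed model for repeated measures. The terms are group, visit, group × visit and the baseline value, with unstructured within-patient covariance. Name the Group 3 minus Group 2 difference at three months as the contrast to report, with its 95% CI.

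Include every patient with at least one post-baseline visit. State that the exclusion of patients who withdraw does not remove values already recorded from this analysis. Without that sentence the model could not use the partial follow-up.

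With six post-baseline visits the covariance has 6 × 7/2 = 21 parameters, so name a simpler structure in advance in case the model does not converge.

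The cost is revised wording in the Statistical analysis section and under the exclusion criteria, plus a little more analysis work. No extra visits, measurements or patients are needed.

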A bottle of Berberine of 500 mg with excipient cbp of 102 tablets each was given, as well as a new bottle at each consultation and the participants handed over the empty bottles or with leftover pills. The way they should ingest them was 3 tablets: 3 times a day before each meal.

Treatment adherence log

The patients will give a treatment adherence log to indicate the day and time they took the tablets, as well as if they did not take them.

Adverse effects log

The patients will give a log in which they should indicate if they had any adverse events, to report them.

Controlled Aerobic Exercise

Controlled aerobic exercise on a treadmill, supervised by a sports physician, the frequency with which participants carried out their sessions was 3 times a week for 30 minutes each, at 60-70% of maximum heart rate. Due to the sedentary lifestyle of the patients, coupled

with obesity and its complications, an 'app' was installed on the participants' cell phones (with the exception of two: one did not have the device and one could not read or write, so they were provided with a semi-automated pedometer so that all participants had the same intervention), all were asked if they exercised, which was denied and their usual physical activity was minimal; in the initial phase of the protocol, their usual physical activity was determined (using the 'app'), which they were instructed to increase, with a goal of 10,000 steps or 150 min per week.

Gene expression

Extraction of total RNA

Blood samples will be lysed, and the material was extracted with TRIzol®Reagent, a mixture of guanidine isocyanate and phenol-chloroform, following the manufacturer's instructions. Once isolated, the total RNA will be suspended in RNase-free water to prevent its degradation and stored at -80°C. 140 µL of peripheral blood were used.

Extraction technique

Sample lysis will be carried out by adding one milliliter of TRIzol reagent and allowing it to incubate for 10 minutes.

1) Separation phase. Phenol-chloroform (0.2 mL per sample) was added, and the mixture was then centrifuged. Three phases were separated: a lower organic phase with the proteins, an interface with the DNA, and a transparent upper aqueous phase with the RNA. This fraction was transferred to a new tube to precipitate the RNA.

2) RNA precipitation by adding 0.5 mL of isopropyl alcohol. Centrifugation at 12,000g for 10 min at 4°C occurs, and the precipitated RNA forms a pellet or adheres to the walls and base of the tube.

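### The only visible intake instruction for Berberine can mean 3 or 9 units of 500 mg a day (1,500 or 4,500 mg), no daily total is stated, and the dose definition and supply rule do not resolve it

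*Combined protocol and SAP*

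**What the plan says.** The section on therapeutic indications, under Phytopharmaceutical, gives the instruction: "The way they should ingest them was 3 tablets: 3 times a day before each meal". It also says that a bottle holds 102 tablets of 500 mg, that a new bottle is given at each consultation, and that participants return their bottles whether or not tablets remain.

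The Variable Description treats Berberine as a quantitative independent variable: "Measurement scale: ratio" and "Measurement unit: 500 mg with excipient q.s". Its operational definition is that "the tested dose of Berberine was 500 mg, given to patients for 3 months". The operational description of the study says the product was supplied "in 500 mg capsules, to treat patients for 3 months", so the same unit is a capsule in one place and a tablet in another.

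Three places bear on the dispensing interval:
- Study groups, Group 3: "moderate aerobic exercise and Berberine phytopharmaceutical. With biweekly sessions for 3 months".
- Nutritional Consultations: "The consultations will be biweekly to evaluate body weight, anthropometry and adherence to the nutritional regimen".
- Anthropometric Evaluation: the variables are "evaluated at the beginning of the program, every 15 days and at the end".

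The adherence log is described as recording the day and time of intake, and missed intakes. It is not said to record the number of tablets taken. No visible section gives a daily total in tablets or milligrams.

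**The concern.** The colon in the intake instruction leaves two natural readings: three tablets a day, one before each of three meals, or three tablets before each of three meals. A participant, or a site repeating the study, could follow the sentence faithfully and arrive at exposures that differ threefold.

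The hypothesis concerns the effect of Berberine on the expression of NLRP3, IL-1β and TNF-α. A result on that hypothesis is hard to interpret or repeat if the reader cannot tell which regimen produced it. Adherence measured by returned tablets has the same problem, because the number that should have been taken is the denominator.

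**Working it through.** The plan states no daily total, so there is no figure to reproduce. The check asks whether the other passages settle the reading.

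**Inputs.** Unit strength 500 mg (Variable Description; therapeutic indications). Bottle of 102 tablets, one at each consultation (therapeutic indications). Interval between consultations 14-15 days, from the biweekly consultations and the 15-day anthropometry. That the dispensing consultation is the biweekly one is inferred.

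**Step 1: daily dose = units per day × 500 mg.**
- 3 a day: 3 × 500 = 1,500 mg.
- 9 a day: 9 × 500 = 4,500 mg.
- Ratio: 4,500 / 1,500 = 3.

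**Step 2: does the 500 mg tested dose decide it?**
- Read per intake, it agrees with one tablet at each intake and conflicts with three (3 × 500 = 1,500 mg per intake).
- Read per day, it conflicts with both readings.
- The definition does not say which is meant.

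**Step 3: does the supply decide it?** Need = units per day × days; balance = 102 − need; days per bottle = 102 / units per day.

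| Reading | Days per bottle | Interval (days) | Need | Balance |
|---|---|---|---|---|
| 3 a day | 34 | 14 | 42 | +60 |
| 3 a day | 34 | 15 | 45 | +57 |
| 9 a day | 11.3 | 14 | 126 | −24 |
| 9 a day | 11.3 | 15 | 135 | −33 |

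At 9 a day one bottle covers at most 102/126 = 81% or 102/135 = 76% of the instructed intake.

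**Step 4: sensitivity to the interval.** If a bottle were given every 28 or 30 days, which no section states:
- 3 a day needs 84 or 90 tablets, leaving 18 or 12.
- 9 a day needs 252 or 270, so the bottle is 150 or 168 short.

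If biweekly meant twice a week (3.5 days), needs would be 10.5 and 31.5 tablets and one bottle would suffice under both readings. The 15-day anthropometry points to the fortnightly sense.

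**Step 5: effect on adherence.** Suppose 42 tablets are gone from a bottle after 14 days. Adherence is 42/42 = 100% under one reading and 42/126 = 33% under the other. The log as described does not separate them, because both readings have three intakes a day.

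**The case against.** The strongest reply is that the text leans one way. One bottle per fortnight can supply 3 a day but not 9, unused tablets are expected back, and a 500 mg dose is compatible with one unit per intake but not with three. The asymmetry is real: a returned surplus breaks no rule in the protocol, whereas nothing in the protocol accommodates a shortfall. So it would be wrong to say that the supply contradicts both readings equally. The sentence about returned bottles is a generic procedure and is evidence against neither reading.

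A reader might go further and infer that the supply establishes the dose. The documents do not support that. The link between bottle and biweekly visit is inferred, the 500 mg carries no frequency, and a dose should not have to be deduced from bottle size.

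Two other replies have weight. The analysis compares groups by ANOVA and t test, not by dose, so neither reading alters a planned test. The consent pages are not available, and participant instructions may have been clearer there. The text also looks translated, so the colon and the capsule/tablet difference may be artefacts. These points limit the consequence, but the visible sections still need reconciling.

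**Conclusion.** The point holds as an ambiguity in the stated regimen, worth a factor of three (1,500 against 4,500 mg a day). The 500 mg definition does not resolve it, and at the inferred 14-15 day interval one of the two readings cannot be met from the stated supply. The main consequence is for reporting, reproducibility and the adherence denominator.

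Two stronger conclusions are tempting and should not be drawn:
- That exposure is wholly undefined. An instruction exists and has two identifiable readings; it is ambiguously stated.
- That participants are at risk now. The Abstract reports outcomes, and the exercise section describes individual participants in the past tense, so the text reads largely as written after treatment, although the section on study subjects uses the future tense. Safety is affected only if dosing continues or the protocol is reused.

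The supply figures assume one bottle per interval, no carry-over, and 500 mg per unit. The two readings of the instruction do not depend on the interval. The conclusion covers the visible text only.

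**What to change.** The sponsor and its clinicians should reconcile the Variable Description, the therapeutic indications and the supply rule into one statement giving dosage form, unit strength, units per intake, intakes per day and total milligrams per day. That statement should replace the present definition of the independent variable. The dispensed quantity should then be confirmed to cover the interval between consultations, with the dispensing visit named. Which figure is right is for the sponsor and its clinicians to say.

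If dosing is complete, report the instruction that participants were actually given. Where returned tablets were counted or kept, check it by dividing the tablets missing from each bottle by the intakes logged for the same period. For example, 45 missing over 45 logged intakes gives 1 per intake, and 102 missing over 34 gives 3.

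The cost is one protocol clarification or, after completion, one reporting statement and a tally of returns against logs. Sample size, visits, laboratory work and planned tests are unchanged.
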